5.2 Identification and description of the Investigational Medical Device

Hemanext ONE is a blood container set used to process and store CPD/PAGGSM Red Blood Cells, Leukocytes reduced, and O_2/CO_2 Reduced. The Hemanext ONE system is an assembly of two disposables: the Oxygen Reduction Bag (ORB) and the Hemanext Storage Bag (HSB).

[figure not shown]
See Figure 3 below for the concept configuration. The larger bag is the ORB and the smaller bag is the HSB.

The ORB consists of the following elements: (a) an inner bag; (b) outer barrier bag; (c) spacer and (d) quilt of 9 sorbent sachets. The inner bag holds the PAGGSM LR RBC and is housed in an outer barrier bag. The outer barrier bag ensures that there is no ingress of oxygen into the ORB during or post O₂ /CO₂ reduction. The inner bag is physically separated from the outer barrier bag by polyester fabric elements surrounding the outer surface of the inner bag. The materials of construction of the inner bag ensure that oxygen released from the LR RBC is transferred to the surrounding space. The sorbent quilt captures and stores oxygen released from the LR RBC. The spacer (perforated patterned polyethylene stabilizer) is placed in the space between the inner bag and the sorbent quilt to ensure that all of the surface area of the inner bag is clear and able to transfer oxygen. The oxygen indicator is designed to change color if exposed to oxygen. The ORB has tubing to allow sterile docking of the LR RBC bag (see Figure 4 below). The ORB is connected to the HSB bag via integral tubing. The connections facilitate the transfer of the oxygen reduced LR RBC blood.

Figure 4: ORB Assembly View

[figure not shown]

The HSB consists of the following elements: (a) inner bag; (b) barrier bag; (c) spacer and (d) single sorbent sachet. Materials of construction of the HSB ensure that it is capable of maintaining the appropriate low oxygen environment for additive stored LR RBC in refrigerated environments for 42 days.

The inner bag holds the blood and is housed inside the oxygen impermeable barrier bag.

A sorbent is placed in the space, between the inner and outer bags, to ensure that low oxygen levels are maintained post reduction by the HSB. See Figure 5 below.

Figure 5: HSB Assembly View

5.2.1 Description of Hemanext Process:

A LR RBC unit bag is connected using a sterile docking device to the ORB. The sorbent quilt between the inner bag and the barrier bag creates an O_2 /CO₂ depleted environment. LR RBC are then transferred by gravity to the ORB inner bag.

Once the full unit volume is in the ORB inner bag; the Hemanext system is transferred to a tray on an agitator (the platelet agitator should operate at 72 cycles/minute) at room temperature (22+2°C). Its contents are evenly distributed, creating a large thin layer of LR RBC contacting the inner surface of the ORB inner bag. The agitator moves in a side to side motion causing the LR RBC to travel within the inner bag in a wave-like motion at the same rate as the shaker, maintaining a constant agitation of RBC and additive solution.

The red blood cells in direct contact with the inner bag surface release oxygen through the material and into the O_2/CO_2 starved environment between the inner bag and barrier bag of the ORB. Maintaining this agitation of red blood cells and residual plasma/additive solution ensures that oxygen on the RBCs that are furthest from the walls of the bag exchange oxygen molecules with

PRO-CLIN-0012 Rev. AB - 16-MAR-2023

low oxygenated solution closest to the bag surface, which in turn lose the gained oxygen by constant exposure to the oxygen-depleted environment on the outer side of the ORB inner bag.

The O_2/CO_2 absorption rate is characteristic of the oxygen reduction container material, exchange surface area, volume of RBC and agitation. At the end of the exposure time of 3 hours (+/- 15 minutes), the resulting deoxygenated LR RBC is transferred to the HSB in the kit. The HSB utilizes the same principles as the ORB to preserve a low oxygen and CO_2 environment within its contents. It utilizes a sorbent to maintain this environment and preserve the blood at low O_2 levels for its storage duration of up to 42 days. The HSB is also a transfusion ready device.

Study ID (Year Initiated)	Study Name	Purpose	Number of Subjects	Outcome
RESPR22 (2016)	RESPR22: OUS Solution Characterization with Hemanext ONE	The purpose of this work was to conduct an operational trial (feasibility study) of this new technology to mimic routine blood product processing and storage for RBC units stored in SAGM and PAGGSM. The data were useful for Hemanext to evaluate the performance of its device for the European market.	32 donors. 8 pools of four donors.	Hemanext ONE hypoxic RBC met all in vitro acceptance criteria. PAGGSM was the additive solution of choice for a CE mark trial.
RESPR27 (2016)	RESPR27: Hemanext ONE with 42-day Storage and in-vitro Characterization of Resultant Oxygen Reduced, Leukoreduced, Red Blood Cells in PAGGSM vs. Control.	The purpose of this pilot study was to generate data of the current design of Hemanext ONE (consisting of an oxygen reduction bag "ORB" and a Hemanext storage bag "HSB", 60" tubing, y-connector and 2 ratchet clamps) and Hemanext ONE process.	20 donors. 10 pools of two donors.	Hemanext ONE hypoxic RBC met all in vitro acceptance criteria.
CLIN-0002 (2017)	CLIN-0002: In Vitro Evaluation of the Hemanext ONE Red Blood Cell Processing System for Leukoreduced Red Blood Cells with CPD Anticoagulant and PAGGSM	The objective of this clinical study was to evaluate CPD/PAGGSM leukocyte-reduced RBC stored anaerobically for 49 days after deoxygenation with the Hemanext ONE	30 donors	The Hemanext ONE process passed all acceptance criteria for overnight room temperature hold with a CPD/PAGGSM set at 42 days.

5.3 Preclinical Evidence

	additive.	Storage System. In addition to hemolysis, a list of standard blood quality parameters were measured.		
CLIN-0001 (2019)	CLIN-0001: Clinical Investigation to Evaluate the Hemanext ONE Oxygen Reduction System for Leukoreduced Red Blood Cells with CP2D Anticoagulant and AS-3 Additive - Pivotal Trial	The primary endpoints that were evaluated in this clinical trial were RBC mass recovery, hemolysis and 24- hour in vivo red cell recovery.	100 donors in crossover design	The data generated in this study passed acceptance criteria to support the license of CP2D/AS-3 Leukocytes Reduced, Hypoxic Red Blood Cells under conditions of 12-hour room temperature hold.

5.4 Clinical Evidence to Date

Fourteen (14) participants received two separate infusions of approximately 10 mL of autologous radiolabeled RBCs during CLIN-0001. One of the infusions was with hypoxic RBCs in AS-3 produced using the Hemanext ONE process and the other transfusion was with conventional RBCs in AS-3. The hypoxic RBCs infused had an overall higher dual-label 24 hour *in vivo* recovery (mean: 89.3, SD: 5.81) than the conventional RBCs (mean: 85.8, SD: 6.12). None of the participants experienced any AE or SAE related to the use of the Hemanext ONE device.

5.5 Justification for the design of the clinical investigation

The Hemanext ONE System received its CE Mark in April 2021. The Hemanext ONE Post Market Clinical Evaluation Plan requires collection of safety and efficacy data for the device. This post market clinical evaluation will begin to inform on the safety of the blood product resulting from processing leukocyte reduced RBCs with the device.

The Hemanext ONE System may be used to manufacture hypoxic RBCs for any patient requiring a blood transfusion. This pilot investigation aims to study safety of hypoxic RBCs in 2 patient groups: acute burn and hematologic malignancies. Burn patients undergoing surgical excision routinely require large quantities of blood to be transfused. Those patients with hematologic malignancies often require regular transfusions.

Participants in the study will be transfused with 2 units of hypoxic blood during scheduled transfusion therapy visits. The remainder of the units required for transfusion will be drawn from traditionally processed red cells. Adverse events will be collected from the Screening visit through either discharge (burn patients), the subsequent transfusion (hematologic malignancies patient), or Day 28, whichever comes first.

Further study of the safety of hypoxic RBCs will include randomized comparator trials in several types of patients requiring blood transfusions such as surgical burn excision, hematologic malignancies, trauma, sickle cell disease and thalassemia.

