7. CLINICAL INVESTIGATION OUTCOMES

7.1 Primary Outcome

Primary Outcome – for both patients groups

Number of participants who experienced an adverse event (all types/grades) within a time frame up to 24 hours following the transfusion and overall up to 7 days (+/- 1 day) after the transfusion.

The type and the grade of each adverse event will be categorized according to:

- Association for the Advancement of Blood and Biotherapies (AABB) technical manual, 20th edition (2020)
- Biomedical Excellence for Safer Transfusion (BEST) Collaborative review Lancet 2016; 388: 2825–36
- Local AEs database (for reference)
- ISO 14155-2020 definitions

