11.2 Assessments of outcomes

Patients will be monitored for adverse events throughout the entirety of their participation in the clinical investigation. Adverse events will be elicited from the patients, the medical record, and an adverse event diary, if applicable. Patients enrolled will undergo standard care for their disease/ illness as prescribed by the Investigators. All procedures will be performed in compliance with the site's established policies and work instructions. No additional assessments will be performed.

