11.2.1 Assessment of primary outcome

Patients will be monitored for adverse events throughout the entirety of their participation in the clinical investigation. Investigators will monitor patients directly for adverse events during their transfusion visit. In addition, patients will be contacted by phone 24 hours and 7 days (+/- 1) after their transfusion visit to record any adverse events they have experienced since their transfusion visit. All adverse events will be recorded in the CRF and they will be assessed according to the instructions in section 12 of the CIP.

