11.2.2 Assessment of secondary outcomes

For all secondary outcomes related to hemoglobin and vital sign measurements the sites will follow their standard practice.

For all secondary outcomes related to AE occurrence, investigators will monitor patients directly for adverse events during their transfusion visit and then patients will be contacted by phone 24 hours and 7 days (+/- 1) after their transfusion visit to record any adverse events they have experienced since their transfusion visit. The patient's chart will also be checked for any AE occurrence after their following transfusion visit or 28 days after their initial transfusion, whichever comes first. All adverse events will be recorded in the CRF and they will be assessed according to the instructions in section 12.

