11.3.5 Second Follow-Up Visit

This visit will occur 7 days (+/- 1) post-transfusion and will be performed over the phone. The following data will be collected:

- Infection occurrence
- Adverse event occurrence
- Concomitant medications
- Device deficiencies
- Patient Diary

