12.2 Documentation and reporting in Medical Device clinical investigations

Device deficiencies and all **adverse events (AE)** including all **serious adverse events (SAE)** are collected, fully investigated and documented in the source document and appropriate CRF during the entire investigation period, i.e. from patient's informed consent until the last CIP-specific procedure, including a safety follow-up period.

- Documentation of AEs (including SAEs) by the PI includes diagnosis or symptoms, start and stop dates of event, event treatment, event resolution, assessment of seriousness and causal relationship to MD and/or investigation procedure (ISO14155).
- Documentation of DDs by the PI includes description of event, start date, investigational device information, action taken with regard to the investigational device, and whether the DD led to an AE. The Sponsor shall review all DDs and determine and document in writing whether they could have led to a SAE (DD with SADE potential) (ISO14155).

The Sponsor provides the CEC with the documentation at their request

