3.3 Clinical investigation outcomes

3.3.1 **Primary outcome**

Number of participants who experienced an adverse event (all types/grades) from transfusion up to 24 hours and 7 days (+/- 1 day) post transfusion.

3.4 Secondary Outcomes:

1. Evaluation of blood pH, pO2, pCO2, HCO3 and base (excess) before, during and after the transfusion (Burn patients group only).

LINK Medical Study ID: HEM001

- 2. Hemoglobin level before the following transfusion
- 3. Frequency of all AEs, including transfusion related AEs up to 7 days (+/- 1) post-transfusion
- 4. AEs up to 28 days after the initial transfusion, or up to subsequent transfusion episode, whichever comes first.
- 5. Frequency of all AEs, from enrollment, up to 7 days (+/- 1 day) post transfusion, through the assessment patient's diary, when applicable.
- 6. Vital signs over the course of the transfusion and up to 15 minutes post-transfusion.

4 Study Design

This is a single center clinical trial of surgical bleeding in burn patients, and chronically transfused patients with haematologic malignancies. Patients are transfused with hypoxic red blood cells manufactured with Hemanext ONE system". The patient groups are burn patients and chronically transfused patients with haematologic malignancies. Patients need to be adults \geq 18. There will be no randomization of Patient s, no blinding, and no comparator.

A first cohort of 5 patients – solely from the hematological malignancies (chronically transfused) group - will be enrolled, transfused and followed-up until their subsequent transfusion or 28 days (+/- 1 day) post-transfusion, whichever comes first. All safety related data from this initial cohort of 5 patients will be reviewed and assessed by the clinical investigation Data Monitoring Committee (DMC). Upon favourable opinion from the clinical investigation DMC, the enrolment of the remaining patients (both groups) will resume until completion.

Each patient is expected to attend 5 visits:

- 1. Visit 1 (Screening): Determine eligibility and obtain baseline data, physical examination, and safety assessments.
- 2. Visit 2 (Transfusion Day):
 - a. Pre-Transfusion: eligibility, hemoglobin, and safety assessments
 - b. Transfusion: transfusion, safety assessments, and device integrity
 - c. Post-Transfusion: safety assessments, hemoglobin, and device integrity
- 3. Visit 3 Follow-Up (24 hours post-transfusion): safety assessments and device integrity

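### Protocol 5.5 can end adverse event collection before Day 7, and the burn schedules leave the Day 7 contact blank, although the primary outcome runs to 7 days in both groups

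*Protocol*

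**What the plan says.** **End of collection.** Protocol 5.5 states that AEs are "collected from the Screening visit through either discharge (burn patients), the subsequent transfusion (hematologic malignancies patient), or Day 28, whichever comes first".

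**Primary outcome.** Protocol 7.1 counts participants in both groups with any AE up to 24 hours and "overall up to 7 days (+/- 1 day) after the transfusion". SAP 3.3.1 counts them "from transfusion up to 24 hours and 7 days (+/- 1 day) post transfusion".

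**Day 7 contact.** Protocol 11.2.1 says "patients will be contacted by phone 24 hours and 7 days (+/- 1) after their transfusion visit", and 11.2.2 repeats the two calls for the secondary AE outcomes. Protocol 11.3.5 adds: "This visit will occur 7 days (+/- 1) post-transfusion and will be performed over the phone", with AE occurrence on its data list. SAP 6.1.1 places the same call at Visit 4. None of these is limited to one group.

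**General rules.** Protocol 11.2: "Patients will be monitored for adverse events throughout the entirety of their participation in the clinical investigation". Protocol 12.2 and 12.6 collect AEs "from patient's informed consent until the last CIP-specific procedure, including a safety follow-up period".

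**Schedules.** In the burn schedules (Synopsis, Protocol 11.1.2, SAP Appendix B) the AE row is marked at Visits 1, 2, 3 and 5. The Visit 4 column is empty throughout. The haematology schedules mark AEs at Visit 4. In the burn schedules, Visits 4 and 5 carry the same title, Follow-Up 2.

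**The concern.** Two current texts can be read as not requiring AE collection across the whole primary window. Protocol 5.5 ties the end of collection to discharge or the next transfusion, and either can come before Day 7. The burn schedules show no AE entry at Day 7.

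The sole primary outcome is a safety count. It records whether each participant had at least one AE, so an unrecorded event can leave the 7-day count unchanged or lower it, but cannot raise it. In a trial meant to detect safety problems, that direction flatters the product. The blank Visit 4 column does not touch the 24-hour count, because the burn schedules mark AEs at Visit 3.

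**Working it through.** There is no powered figure to reproduce: Protocol 13.1 states no hypothesis, and SAP 5.1 gives no statistical basis for 20 patients. The check is a comparison of texts.

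**Step 1. When does AE collection end?**

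| Place | Burn | Haematology |
|---|---|---|
| Protocol 5.5 | Discharge or Day 28, the earlier | Next transfusion or Day 28, the earlier |
| Protocol 6.3 (secondary objective) and 11.3.6 (Visit 5) | Next transfusion or Day 28, the earlier | Same |
| Protocol 7.1, SAP 3.3.1 (primary window) | At least to Day 7 (+/- 1) | Same |
| Protocol 11.2, 12.2, 12.6 | Throughout participation, to the last protocol-specific procedure | Same |
| Protocol 13.5 (drop-outs after transfusion) | Covers the 7 days (+/- 1) first; the next-transfusion stop applies only beyond that | Same |

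Only 5.5 can end AE collection as a whole before Day 7. For burn patients it also names a different stopping event (discharge) from 6.3 and 11.3.6.

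**Step 2. Are AEs taken at Day 7?** Protocol 11.2.1, 11.2.2 and 11.3.5 and SAP 6.1.1 say yes for everyone. The haematology schedules agree. The three burn schedules do not. The gap recurs in three burn tables across two documents and is filled in the haematology tables, so a text-extraction fault is unlikely. The duplicated title suggests a drafting slip.

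**Step 3. Can Visit 5 cover the gap?** It draws on the chart: "The patient's chart will also be checked for any AE occurrence after their following transfusion visit or 28 days after their initial transfusion". But Visit 5 falls on the day of the next transfusion if that precedes Day 28, which can be at or before Day 7. Protocol 5.1.5 describes roughly weekly transfusion in intensive haematology treatment. Protocol 5.1.4 describes post-operative bleeding over several days in burn patients, with further transfusion. A Visit 5 that early cannot capture later events in the window. Nothing cancels the Day 7 call in that case, but nothing says explicitly that it is still made.

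**Step 4. Size per missed patient.** Inputs: 10 patients per group and 20 in total (Protocol 13.2, SAP 5.1), all transfused.

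- Group: 1/10 = 10 percentage points.
- Total: 1/20 = 5 percentage points.
- If the Day 7 call is made in every patient: no loss from this source.

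The number of such patients cannot be calculated. The documents give no 7-day AE rate and no length of stay for these patients. The only re-transfusion interval is the approximate one in Protocol 5.1.5.

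**The case against.** The strongest reply is that the operative sections are clear. Four of them require the Day 7 call, while 5.5 is design justification rather than a procedure. A site following sections 11.2 and 11.3 loses nothing. There are also other routes to an event: the medical record (11.2), the Visit 5 chart check (11.2.2, 11.3.6), the attempted contact of drop-outs (13.5), and the diary. The Synopsis lists the diary as part of the intervention for both populations, and 6.3 makes diary-reported AEs an objective for both. All of this stands, and it makes the loss conditional. It does not remove the contradiction. The diary is qualified as applying only where applicable (7.2, 11.2) and has no row in the burn schedules. The chart check can come too early, as Step 3 shows.

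A reader might infer three stronger things that the documents do not support.

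- *That the burn schedules shorten AE collection.* They mark AEs again at Visit 5, so they do not contradict 11.2, 12.2, 12.6 or 13.5. Their conflict is confined to the Day 7 contact.
- *That the SAP classes a patient not followed to Day 7 as a non-event.* No such rule is written. SAP 7.1.1 keeps patients with missing data in the denominator, but also says that numbers with missing values will be presented. SAP 7.1.5 is silent on incomplete 7-day follow-up. That the count cannot rise follows from how it is formed, not from a stated imputation.
- *That the analysis could not reveal the gap.* SAP 7.3 summarises attendance at each visit and SAP 7.1.1 presents results by group. Visit 4 attendance therefore largely shows how many patients were contacted at Day 7.

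**Conclusion.** The contradiction is real and should be fixed. Protocol 5.5 can close AE collection before Day 7 in either group. This conflicts with the primary outcome, the required Day 7 call and the general collection rules. It also gives burn patients a different stopping event from the rest of the protocol. The burn schedules separately omit the Day 7 AE assessment that the text requires.

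The consequence is possible under-recording, not demonstrated loss. It arises only if a site follows 5.5 or the burn schedule in place of the Day 7 call, and the other sources then fail to recover the event. Each patient whose only AE in the window is missed lowers the 7-day result by 10 points in the group and 5 points overall, assuming the planned 10 and 20 patients are transfused. The number of such patients is unknown. The study is descriptive and unpowered, so no test or power figure is affected.

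**What to change.** Reconcile Protocol 5.5 and the three burn schedules with Protocol 7.1, 11.2.1 and 11.3.5 and SAP 6.1.1:

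1. State that AEs are collected to Day 7 (+/- 1) in every transfused patient, regardless of discharge or re-transfusion, and that any earliest-of stopping rule applies only after that.
2. State one end-of-collection rule for burn patients, used identically in 5.5, 6.3 and 11.3.6.
3. State that the Day 7 call is made even if Visit 5 has already taken place.
4. Complete the Visit 4 column in the burn schedules (Synopsis, 11.1.2, SAP Appendix B) to match 11.3.5: AEs, concomitant medications, and the diary where applicable. Correct the duplicated Follow-Up 2 title.
5. Optionally, show the Visit 4 attendance already planned in SAP 7.3 beside the 7-day AE count in SAP 7.8.1.

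The cost is wording and table entries, handled through a protocol amendment under Protocol 4.9 and a matching SAP update. The Day 7 call is already planned, so no visit or procedure is added.

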	 Transfusion of two units of Red Blood Cells, Leukocytes reduced, O₂/CO₂ reduced (single transfusion course) manufactured with the Hemanext ONE System, combined with PRN standard Red Blood Cells, as applicable. Patient's diary
Control intervention (if applicable):	Not applicable
Number of subjects with rationale:	10 acute burn patients and 10 patients with haematological malignancies, who require transfusion of red cells concentrates and who fulfil all eligibility criteria will be enrolled in this clinical investigation at Haukeland University Hospital.
	A total of twenty patients will be sufficient to assess preliminary safety of O ₂ /CO ₂ reduced RBCs, as the standard rate of transfusion related adverse events is usually low and these expected events are well known. If any unexpected adverse events (any type or grade) should occur, they will be identified as such.
Duration of the investigation:	This clinical investigation is estimated to last for a period of approximately 6 months.
Investigation	Anticipated Start Date: May – June 2022
schedule:	Anticipated End Date: November – December 2022
Investigator(s):	Principal Investigator: [name]
	Address: Haukeland University Hespital [name]
	Haukeland University Hospital, [name]
	Norway
	Phone:
	E-mail:

	Sub-Investigator: [name] Address : Haukeland University Hospital, [name] Norway E-mail:
Investigational Site(s):	This clinical investigation will only involve one single clinical site:
	Haukeland University Hospital [name] Norway
Blood Bank	Oslo: Address: Department of Immunology and Transfusion Medicine Section for Blood processing Oslo University Hospital Ullevål Norway
	Bergen: Address:
	Address: Haukeland University Hospital Department of Immunology and Transfusion Medicine [name] Norway E-mail:
Data Monitoring Committee (DMC)	Membership: Professor of intensive care medicine

	Haukeland University Hospital, Bergen
	Chief of Burns, Plastic and reconstructive surgeon
	Haukeland University Hospital, Bergen
	Pland Pank, Haukaland University Heanital, Person
	Blood Bank - Haukeland University Hospital, Bergen
	Blood Bank - Haukeland University Hospital, Bergen
	Blood Bank - Haukeland University Hospital, Bergen
Statistical considerations:	This clinical investigation is not statistically powered – only descriptive statistical methods will be applied

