6.2 Primary Objective

Primary Objective – for both patients groups

Hypoxic RBCs safety and tolerance assessment up to 24 hours following the transfusion initiation and overall up to 7 days (+/- 1 day) after the transfusion episode (single transfusion course).

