Appendix A: Clinical investigation flow chart Hematogical Malignancies Group:

| Investigation Periods | Screening & Enrollmen t Visit | Pre- Transfusion | Transfusion | Post- Transfusion | Follow Up 1 | Follow-up 2 | Follow-up 3 |
|---|--|---------------------|-------------|----------------------|-------------|-------------------|--|
| Visit | 1 | 2 | 2 | 2 | 3 | 4 | 5 |
| Time (hour, day, week) | D0 | D1 | D1 | D1 | D2 (≤ 24h) | D7 (+/- 1 day) | Day of subsequent transfusion or D28, whichever comes 1 st |
| In- /Exclusion Criteria | х | х | | | | | |
| Patient Information | | | | | | | |
| Patient consent (ICF) | х | | | | | | |
| Demographics | x | | | | | | |
| Medical History | х | | | | | | |
| Concomitant Medications | x | x | x | x | x | x | х |
| Physical Examination | х | | | | | | x |
| Pregnancy Test | х | | | | | | |
| Height | x | | | | | | |
| Weight | x | | | | | | |
| RBC Unit Weight | | x | | | | | |
| Patient Hemoglobin | | x | | x | | | x |
| Blood Pressure | x | x | x | x | | | |
| Heart Rate | x | x | x | x | | | |
| Body Temperature | x | x | x | x | | | |
| Respiratory Rate | x | x | x | x | | | |
| Oxygen Saturation | x | x | x | x | | | |
| Transfusion | | | x | | | | |
| Adverse Events, Adverse device effects | x | x | x | x | x | x | x |
| Review Device Integrity | | x | x | x | | | |
| Patient Diary | x | x | x | x | x | x | |

LINK Medical Study ID: HEM001

| Appendix B: | Clinical investigation | flow Burn patients Group: |
|-------------|------------------------|---------------------------|
|-------------|------------------------|---------------------------|

| Investigation Periods | Screening & Enrollment Visit | Pre- Transfusio n | Transfusion | Post- Transfusion | Follow Up 1 | Follow-Up 2 | Follow-Up 2 |
|--|---------------------------------------|-------------------------|-------------|----------------------|-------------------|----------------------|--|
| Visit | 1 | 2 | 2 | 2 | 3 | 4 | 5 |
| Time (hour, day, week) | Day 0 | Day 1 | Day 1 | Day 1 | Day 2 (≤ 24 h) | Day 7 (+/- 1 day) | Day of subsequent transfusion or D28, whichever comes 1 st |
| In- /Exclusion Criteria | x | | | | | | |
| TBSA | x | | | | | | |
| Patient Information | | Γ | Γ | Γ | | | |
| Patient information and consent (ICF) | x | | | | | | |
| Demographics | x | Γ | Γ |   |   | | |
| Medical History | х | | | | | | |
| Concomitant Medications | x | x | x | x | x | | x |
| Physical Examination | x | | | | | | x |

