| Pregnancy Test | x | | | Τ | | | |
| Height | x | | | | | | |
| Weight | x | | | | | | |
| RBC Unit Weight | | x | | | | | |
| Patient Hemoglobin | | x | | x | | | х |
| Blood Pressure | x | x | x | x | | | |
| Heart Rate | x | x | x | x | | | |
| Body Temperature | x | x | x | x | | | |
| Respiratory Rate | x | x | x | x | | | |
| Oxygen Saturation | x | x | x | x | | | |
| Transfusion | | | x | | | | |
| Adverse Events, Adverse device effects | x | x | x | X | x | | x |
| Review Device Integrity | | x | x | x | | | |

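### Protocol 5.5 ends burn adverse-event collection at discharge and the burn schedules have no Day 7 adverse-event mark, so the 7-day primary count in burn patients can be left incomplete

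*Protocol*

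**What the plan says.** **Stop rule in the rationale.** Protocol 5.5 collects adverse events from screening "through either discharge (burn patients), the subsequent transfusion (hematologic malignancies patient), or Day 28, whichever comes first". It gives each patient group its own stop and sets no minimum period.

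**Primary outcome.** Protocol 7.1 counts participants with an adverse event "within a time frame up to 24 hours following the transfusion and overall up to 7 days (+/- 1 day) after the transfusion", for both groups. SAP 3.3.1 uses the same two windows.

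**Day 7 contact.** Protocol 11.2.1 says "patients will be contacted by phone 24 hours and 7 days (+/- 1) after their transfusion visit to record any adverse events", without restriction to one group or to inpatients. Protocol 11.3.5 repeats it ("This visit will occur 7 days (+/- 1) post-transfusion and will be performed over the phone") and lists adverse events among the data collected. SAP 6.1.1 has the same call.

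**Schedules.** The haematology row in SAP Appendix A reads "Adverse Events, Adverse device effects | x | x | x | x | x | x | x". The burn row in SAP Appendix B reads "Adverse Events, Adverse device effects | x | x | x | X | x | | x". The empty cell is Visit 4, Day 7. The burn schedules in the protocol synopsis and in 11.1.2 have the same blank.

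**Index episode.** Protocol 6.2 sets the period as "overall up to 7 days (+/- 1 day) after the transfusion episode (single transfusion course"). The synopsis describes the intervention as two hypoxic units "combined with PRN standard Red Blood Cells, as applicable". Neither document states when that course closes for a burn patient.

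**The concern.** The primary outcome is a count of affected patients within fixed windows, so it depends on adverse events being sought over the whole window in everyone. For burn patients the plan gives two incompatible ends to collection, and one of them can fall inside the 7-day window. The schedule might have been expected to settle the matter, but for burn patients it shows no adverse-event assessment on Day 7.

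An event that is not sought cannot appear in the SAP 7.8.1 counts or in the individual listings. With 10 burn patients and no comparator, one missed patient changes the group percentage by 10 points (1/10). Protocol 13.5 pursues drop-outs through 7 days and beyond, so under 5.5 read literally a patient who dropped out would be followed for longer than a compliant burn patient who went home early.

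**Working it through.** The plan gives no figure to reproduce here: the study has no hypothesis (Protocol 13.1), and the 10 + 10 = 20 patients have no statistical basis (SAP 5.1). The check is a comparison of texts followed by one subtraction.

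**Step 1. End of adverse-event collection for a burn patient, by source**

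| Source | End stated | Discharge mentioned? |
|---|---|---|
| Protocol 5.5 | discharge or Day 28 | yes |
| Protocol synopsis objectives and 6.3 (both groups) | next transfusion or Day 28 | no |
| Protocol 11.1.2, Visit 5 (burn) | next transfusion or Day 28 | no |
| Protocol 11.2.2 and 11.3.6 | next transfusion or Day 28 | no |
| Protocol 13.5 (drop-outs) | 7 days, then next transfusion or Day 28 | no |
| SAP 3.2 and 3.4 | next transfusion or Day 28 | no |
| SAP Appendix B, Visit 5 (burn) | next transfusion or Day 28 | no |

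Protocol 5.5 stands alone. It is also the only rule whose burn-specific trigger can fall before Day 7 with nothing in the same passage to protect the primary window.

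**Step 2. Day 7 adverse-event assessment**

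| Source | Haematology | Burn |
|---|---|---|
| Protocol 11.2.1, 11.3.5; SAP 6.1.1 (text) | required | required |
| Protocol synopsis schedule | marked | blank |
| Protocol 11.1.1 / 11.1.2 | marked | blank |
| SAP Appendix A / B | marked | blank |

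The blank is the same in all three burn schedules. No row of those schedules has a Visit 4 mark, so the column exists but prescribes nothing.

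**Step 3. Size under the literal reading**

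Let d be the discharge day counted from the index transfusion. The documents do not give d, so it is an assumption.

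- Day 7 call not made: primary-window days lost = max(0, 7 − d).
- Day 7 call made, as 11.2.1 requires: days lost = 0.

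| d | Lost without the call | Share of 7 days | Lost with the call |
|---|---|---|---|
| 1 | 6 | 86% | 0 |
| 3 | 4 | 57% | 0 |
| 5 | 2 | 29% | 0 |
| 7 or later | 0 | 0% | 0 |

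The number of burn patients affected could be anything from 0 to 10 of 10.

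**Step 4. When the burn index episode ends**

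Protocol 5.1.4 expects post-operative bleeding to need further transfusion over several days, so a ward unit on, say, day 3 has to be classed either as part of the index course or as the next transfusion. SAP 6.2.2 helps. For burn patients at Visit 2 it pairs pre-, intra- and post-operative blood gases with before, during and after transfusion. The post-transfusion haemoglobin, due 15 to 60 minutes after the transfusion (Protocol 11, SAP 6.2.1), also needs an end that can be identified that day. Both point to the operative session, but neither document says so.

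**The case against.** The strongest reply is that 5.5 is a rationale section and nothing operative implements a discharge stop. Protocol 11.2.1 and 11.3.5 and SAP 6.1.1 require the Day 7 call, which works just as well once the patient is at home. Protocol 12.2 collects adverse events until the last protocol procedure, and 13.5 follows even drop-outs. The study is small and descriptive, and every recorded event is listed. This stands to the extent that loss of primary data is conditional and is not the expected result. It does not remove the problem, because the burn schedule in 11.1.2 is operative text and it omits the same assessment.

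Four stronger readings are tempting, and the documents do not support them.

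- *A discharge on day d costs 28 − d days of follow-up.* The competing rule also stops at re-transfusion, so 28 days is the wrong benchmark. With the Day 7 contact kept and re-transfusion on day t, the loss is max(0, max(7, min(t, 28)) − d). For d = 5 and t = 10 it is 10 − 5 = 5 days, not 23. For d = 14 and t = 3 the discharge rule collects 14 − 7 = 7 days more than the other rule.
- *Burn patients go 27 days (28 − 1) without ascertainment.* That counts the distance between table marks at Visits 3 and 5. The text requires the Day 7 call, and 11.2.2 and 11.3.6 add a chart review for adverse events at the end of follow-up.
- *The end of the index course is wholly open.* SAP 6.2.2 implies the operative session. What is missing is a plain statement.
- *Burn follow-up must run to Day 28 regardless of re-transfusion.* Stopping at re-transfusion is a defensible choice for attribution, and statisticians could reasonably differ on it.

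**Conclusion.** The inconsistency is real and should be corrected. Protocol 5.5 contradicts both the 7-day primary outcome and the follow-up end used in the rest of the plan, and all three burn schedules omit the Day 7 adverse-event assessment that the text requires. If a site follows either, up to 7 − d days of the primary window are lost for a burn patient discharged on day d before Day 7: 4 of 7 days at d = 3. If the required call is made, nothing in the primary window is lost. The size rests on assumed discharge days and on whether the call is made; the documents give neither discharge days nor the number affected. The missing definition of the burn index episode is a lesser gap, because SAP 6.2.2 already points to the answer.

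**What to change.** 1. In Protocol 5.5, delete the discharge stop and use the next-transfusion-or-Day-28 end found in the rest of the plan. State that adverse events are collected through at least the Day 7 (+/- 1) contact in every transfused patient, regardless of discharge or re-transfusion.
2. Add the Visit 4 adverse-event mark to the burn schedules in the protocol synopsis, Protocol 11.1.2 and SAP Appendix B.
3. State once that the burn index episode is the red-cell units given in the operative session at Visit 2, as SAP 6.2.2 implies, so that a later ward unit counts as the subsequent transfusion. Change 1 then ensures that a ward unit given before Day 7 does not end adverse-event collection early.

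Two loose statements can be aligned at the same time: Protocol 7.2 outcome 5, which gives 28 days as the earlier of two ends without naming the other, and SAP Section 4, which lists Visit 5 as Day 28 only.

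The cost is wording. No visit, blood draw or contact is added, because the Day 7 call is already required.
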